#### **4.8.5 Rationale for the innate, early adaptive and mucosal sampling timepoints**

Examining the effects that the two adjuvants have on a variety of immune responses relative to each other and to the unadjuvanted protein is an important goal of this study.

Systemic innate immune responses will be measured on Day 1 and Day 3 following the vaccination when participants are first exposed to protein ± adjuvants. For Groups 1, 2, and 4, this represents Day 1 and Day 3 following the third vaccination. For Group 3, this sampling will take place on Day 1 and Day 3 following the first vaccination.

For Groups 1, 2, and 4, early systemic adaptive immune responses will be measured in samples collected at Day 0, Month 0.25, Month 3.25, Month 6.25, and Month 12.25. For Group 3, these samples will be collected at Day 0, Month 0.25, Month 6.25, and Month 12.25. These samples will provide both baseline and postvaccine information.

Systemic and mucosal samples collected at Day 0 provide the baseline values prior to vaccination while those collected at Month 6.5 provide data on peak vaccine-induced mucosal and systemic adaptive immune responses.

Finally, collection at Month 18 will provide the opportunity to assess the durability of mucosal and systemic humoral immune responses 6 months after the last vaccination.

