### **9.3 Enrollment and vaccination visits**

Enrollment is simultaneous with first vaccination. The time interval between randomization and enrollment should not exceed 4 working days. The HVTN CRS registers the participant by scheduling the day 0 visit (enrollment) via the Web-based randomization system, and requests the randomization assignment. Circumstances may require a participant's enrollment visit to be changed. This may exceed the 4-day randomization time limit.

At all vaccination visits, the following procedures are performed before vaccination:

- Abbreviated physical examination, including weight, vital signs, and a symptom-directed evaluation by history and/or appropriate physical exam based on participant self-reported symptoms or complaints;
- Assessment of baseline reactogenicity parameters;
- Assessment of concomitant medications (as described in Section 9.2);
- Assessment of any new or unresolved AEs/intercurrent illnesses; and
- Urine or serum pregnancy test (for participants who were born female). Persons who are NOT of reproductive potential due to having undergone total hysterectomy or bilateral oophorectomy (verified by medical records), are not required to undergo pregnancy testing.

Following completion of all procedures in the preceding list, and if results indicate that vaccination may proceed, vaccination is prepared and administered (see Sections 8.3 and 8.4).

Administration of all injections during a vaccination visit must be accomplished within 1 calendar day.

Immediately following vaccination, the participant remains in the clinic for observation. An initial reactogenicity assessment is made at a target of 30 minutes after injection, with an acceptable range of 25-60 minutes. Before leaving the clinic, the participant may be given the postvaccination memory tool and instructed on how to complete it. The site will make arrangements to obtain daily reports of reactogenicity events from the participant during the reactogenicity period (as described in Section 9.10).

The following procedures will be performed at all vaccination visits. These procedures may be performed prior to or following vaccination:

- Risk reduction counseling (as described in Section 9.7);
- Pregnancy prevention assessment (as described in Section 9.2 and 9.8); and

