- Assessment of new or unresolved social impacts (site staff will ask participant about the status of any unresolved social impacts and if s/he has experienced any new social impacts as a result of the trial participation).

Additional procedures will be performed at scheduled visits as specified in Appendix J, Appendix K, Appendix L, and Appendix M:

- HIV infection assessment including pretest counseling. A subsequent follow-up contact is conducted to provide post-test counseling and to report results to participant;
- Confirm that participants received HIV test results from previous visit. If not, provide test results and post-test counseling as appropriate; and
- Administration of the social impact assessment questionnaire (types of impacts assessed involve personal relationships, health insurance, life insurance, educational or employment opportunities, housing, immigration, or travel);
- Administration of behavioral risk assessment questionnaire;
- Specimen collection (blood/mucosal/stool) should be completed prior to vaccination (see Appendix F, Appendix G, Appendix H, and Appendix I);
- For participants who agree to join and who have been randomized to the innate/mucosal subset (see Section 9.5):
  - Urine test for gonorrhea and chlamydia;
  - Vaginal swab for Trichomonas and bacterial vaginosis (for participants providing cervical samples);

- Vaginal swab (if indicated) for hyphae/budding yeast (for participants providing cervical samples);
- Mucosal specimen collection;
- Syphilis serology.

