- Item 25 Revised in Appendix A, *Sample informed consent form*: Maximum blood draw volume
- Item 26 Updated in Appendix A, *Sample informed consent form*: HVTN protocol template text
- Item 27 Updated in Appendix C: Language concerning approved birth control methods
- Item 28 Updated in Appendices A and E: Consent language regarding “other uses” of stored samples
- Item 29 Updated in Appendix A, Item 26: Study-related injury language
- Item 30 Added to “Questions” section in Appendices A and E: Contact titles, IRB/EC name, document references, and MCC contact information
- Item 31 Adjusted in Appendices F through I: Blood draw volumes for laboratory assays
- Item 32 Revised in Appendices F through I: Endpoint laboratory designations
- Item 33 Clarified in footnotes to Appendices J through M: Window for blood and specimen collection prior to vaccination at Visits 2 and 17
- Item 34 Added as Appendix O: Protocol signature page
- Item 35 Corrected in Clarification Memo 1 to protocol Version 2.0
- Item 36 Clarified in Clarification Memo 2 to protocol Version 2.0
- Item 37 Minor typographical, formatting, and cross-reference errors have been corrected throughout the protocol document

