h Urine testing for Chlamydia and gonorrhea will be done only if the participant consents to provide mucosal samples. Specimen collection for this testing will take place at the time of mucosal sampling, prior to vaccination (if scheduled).

i This testing will be done for participants providing cervical mucosal samples. Specimen collection for this testing will take place at the time of mucosal sampling, prior to vaccination (if scheduled).

j This testing will be done for participants providing cervical mucosal samples only if clinically indicated. Specimen collection for this testing will take place at the time of mucosal sampling, prior to vaccination (if scheduled).

k Blood draws and other sample collection required at vaccination visits must be performed prior to administration of study product; however, it is not necessary to have results prior to administration, except for results of a urine or serum pregnancy test, if indicated (see footnote "f"). Blood draws and other samples may be collected within the 14 days prior to vaccination.

l Reactogenicity assessments performed daily for at least 3 days postvaccination (see Section 9.10).

m Collect dietary, antibiotic use, and gastrointestinal symptom information from participants providing stool specimen.

n Optional stool specimen must be collected prior to first vaccination.

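### Group 3's only innate baseline may be drawn up to 14 days before its first dose, while Groups 1, 2 and 4 have a pre-dose innate draw at D84 outside that allowance

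*Combined protocol and SAP*

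**What the plan says.** Section 4.8.5 sets the innate timepoints: "Systemic innate immune responses will be measured on Day 1 and Day 3 following the vaccination when participants are first exposed to protein ± adjuvants". In Groups 1, 2 and 4 that is the third vaccination (D84, Visit 8). For the concurrent arm: "For Group 3, this sampling will take place on Day 1 and Day 3 following the first vaccination". The same section says: "Systemic and mucosal samples collected at Day 0 provide the baseline values prior to vaccination".

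Footnote k of Appendix M (Group 3 subset), repeated in Appendix K (Groups 1, 2 and 4 subset), first fixes the order: "Blood draws and other sample collection required at vaccination visits must be performed prior to administration of study product". It then adds the allowance: "Blood draws and other samples may be collected within the 14 days prior to vaccination". In both appendices k is attached to the headers of Visits 02 and 17 only. The version history for Version 3.0 describes the same scope: "Window for blood and specimen collection prior to vaccination at Visits 2 and 17". Visit 8 carries no such mark. For vaccination visits in general, Section 9.3 says: "Specimen collection (blood/mucosal/stool) should be completed prior to vaccination".

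Section 9.3 also limits the lead time from randomization: "The time interval between randomization and enrollment should not exceed 4 working days". It allows this limit to be exceeded when an enrollment visit is moved.

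**The concern.** Innate readouts such as serum cytokines and whole-blood RNA are meant to show change over one to three days, and Section 10.6.2 plans to look at gene-expression change over time. The value of such a change depends on how close the baseline is to the dose. In Group 3 the single baseline falls at one of the two visits where the draw may be brought forward by two weeks. In Groups 1, 2 and 4 the draw next to the challenge dose falls at a visit with no such allowance.

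A Group 3 sample taken early, for example during a cold that clears before D0, would make the Day 1 and Day 3 changes noisier. There is no second baseline to fall back on, and the sample cannot be retaken once the dose is given. Section 6 has no rule for baseline age. Section 6.4.4.1 drops specimens collected outside the visit window, but a draw that the footnote permits would not obviously be caught by that.

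**Working it through.** **Step 1. Which visits carry innate draws.** The innate rows of the laboratory tables are hard to read by column, so I used the row and visit totals.

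- Group 3 subset (Appendix I): cytokines 34 / 8.5 = 4 draws; RNA 12 / 3 = 4 draws (D0, D1, D3, D7). Visit 2 adds up with one innate set: 5 + 5 + 17 + 42.5 + 17 + 8.5 + 8.5 + (8.5 + 3 + 8.5) + 34 + 8.5 = 166 mL, as stated. Visit 8 is 10 mL, HIV diagnostics only.
- Groups 1, 2 and 4 subset (Appendix G): cytokines 43 / 8.5 ≈ 5 draws; RNA 15 / 3 = 5 draws (D0, D84, D85, D87, D91). Visit 8 adds up only with the innate tubes: 10 + 5 + 17 + (8.5 + 3 + 8.5) = 52 mL, as stated, against 32 mL without them.

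Group 3 thus has one innate draw before its challenge (Visit 2, under the allowance). The other groups have two: Visit 2 under the same allowance, and Visit 8 outside it.

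**Step 2. Largest permitted gap.**

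| | Baseline next to challenge | To Day 1 | To Day 3 |
|---|---|---|---|
| Group 3 | Visit 2, up to 14 days early | 14 + 1 = 15 days | 14 + 3 = 17 days |
| Groups 1, 2, 4 | Visit 8 (D84), same visit as dose | 1 day | 3 days |

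**Step 3. Possible effect on precision.** The documents give no correlations, so these are assumptions. With equal variance σ² at both times, a change score has variance 2σ²(1 − r).

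- Same-day baseline, r = 0.8: 2σ²(0.2) = 0.4σ².
- Older baseline, r = 0.7: 0.6σ², ratio 0.6 / 0.4 = 1.5.
- Older baseline, r = 0.5: 1.0σ², ratio 1.0 / 0.4 = 2.5.

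In a Group 3 versus Group 1 contrast with 18 per arm, only the Group 3 term grows: (1 + 1.5) / 2 = 1.25 and (1 + 2.5) / 2 = 1.75. The difference detectable with 80% power at two-sided 0.05 is 2.80 × √(sum of the two variances / 18):

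- both arms same-day: 2.80 × √(0.8 / 18) = 0.59σ
- Group 3 at r = 0.7: 2.80 × √(1.0 / 18) = 0.66σ
- Group 3 at r = 0.5: 2.80 × √(1.4 / 18) = 0.78σ

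These figures assume that all 18 Group 3 baselines are early. If half are, Group 3's average ratio is 1 + 0.5 × (0.5 to 1.5) = 1.25 to 1.75, and the contrast's is 1.13 to 1.38.

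**Step 4. Interaction with randomization.** The Visit 2 totals differ by group: 204 mL in Appendix G, 166 mL in Appendix I. A site drawing the full set before randomization cannot know which table applies. The innate tubes are the same in both (8.5 + 3 + 8.5 = 20 mL). The difference lies in stored PBMC (68 against 34 mL), stored serum (17 against 8.5 mL) and Group 3's 5 mL CBC: 34 + 8.5 − 5 = 37.5, against 204 − 166 = 38 with rounding.

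**The case against.** A reader might infer that Group 3's changes are not measured from a pre-dose state. The documents do not support that. Footnote k requires the draw to come before the product, so even a Day −14 sample is vaccine-naive, and the early draw is optional. Section 4.8.5 itself speaks of samples collected at Day 0.

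A reader might also infer that a licensed inactivated vaccine given in the gap would be counted as a study-vaccine effect. Exclusion criterion 9 bars such vaccines in the same 14 days, and criterion 8 bars live vaccines other than influenza for 30 days. Section 9.3 requires a check for intercurrent illness before each dose, and Section 7.3.1 lists symptoms that could mask a reaction as grounds for delay. What remains is an illness already over by D0.

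If tubes follow the assigned-group table, the draw comes after randomization and the gap is usually a few working days. That is a fair inference, but it is not stated: Section 9.3 allows exceptions, footnote k does not refer to it, and the innate tubes do not depend on the assignment.

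The innate assays are exploratory (Section 5.3), Section 6 plans no innate Group 3 versus Group 1 test, and that contrast is confounded in any case because Group 1's D84 baseline follows two ALVAC doses. The comparison of the adjuvants with each other and with the unadjuvanted protein uses Groups 1, 2 and 4 and is untouched. All of this stands and limits the weight of the point.

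Finally, visit windows are in the Study Specific Procedures and collection guidance is in the Site Lab Instructions. Neither was available, and either could already require a same-day draw.

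**Conclusion.** The point holds as a limited one. The plan permits Group 3's only innate baseline to be up to 14 days old, with gaps of up to about 15 and 17 days to the Day 1 and Day 3 samples. Groups 1, 2 and 4 have a D84 draw outside that allowance. The harm is added within-person noise and unequal baseline timing in an exploratory endpoint. No primary or secondary result is affected.

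The size is unknown. With correlations assumed to fall from 0.8 to between 0.5 and 0.7, Group 3's change-score variance rises 1.5 to 2.5-fold and a Group 3 versus Group 1 contrast's variance 1.25 to 1.75-fold, and only if all 18 are drawn early. A reader might turn the first range into 18 participants shrinking to between 7 and 12 (18 / 2.5 and 18 / 1.5). That describes Group 3 alone in the worst case; for the contrast the equivalent is about 10 to 14 per arm (18 / 1.75 and 18 / 1.25). Nor do the documents show a systematic shift: drift without a time trend adds noise, not bias.

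The change is still worth making. It is cheap, a poor Group 3 baseline cannot be recovered after dosing, and nothing in the documents reviewed requires a D0 innate draw or adjusts for baseline age.

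**What to change.** Amend footnote k in Appendices K and M so that the Visit 2 allowance does not cover the innate tubes (serum cytokines, RNA gene expression, innate phenotyping) or the paired Group 3 CBC. Draw these on D0 before vaccination, and keep the allowance for all other samples. Both appendices need the sentence because the assignment may not be known when an early draw is made.

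Cost: one sentence in each of two footnotes. Participants who used the early draw give about 20 mL on D0 (8.5 + 3 + 8.5), plus 5 mL for the CBC in Group 3, at a visit they already attend. Total blood volume is unchanged. The change aligns baseline timing only; it does not remove the difference in prior ALVAC exposure between Group 3 at D0 and the other groups at D84.

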## Appendix N Adverse events of special interest

AEs of special interest (AESI) for this protocol include but are not limited to potential immune-mediated diseases; representative examples of AESI are listed below. Updates to AESI will be provided as an appendix to the *HVTN 107 Study Specific Procedures*

Neuroinflammatory disorders	Musculoskeletal disorders	Skin disorders

 
• Cranial nerve disorders, including paralyses/paresis (eg Bell's palsy)
 
• Optic neuritis
 
• Multiple sclerosis
 
• Transverse myelitis
 
• Guillain-Barré syndrome, including Miller Fisher syndrome and other variants
 
• Acute disseminated encephalomyelitis, including site specific variants: eg non-infectious encephalitis, encephalomyelitis, myelitis, myeloradiculoneuritis
 
• Myasthenia gravis, including Lambert-Eaton myasthenic syndrome
 
• Immune-mediated peripheral neuropathies and plexopathies, (including chronic inflammatory demyelinating polyneuropathy, multifocal motor neuropathy and polyneuropathies associated with monoclonal gammopathy).
 
• Narcolepsy
 
	
 
• Systemic lupus erythematosus and associated conditions
 
• Systemic scleroderma (Systemic sclerosis), including diffuse systemic form and CREST syndrome
 
• Idiopathic inflammatory myopathies, including dermatomyositis
 
• Polymyositis
 
• Antisynthetase syndrome
 
• Rheumatoid arthritis, and associated conditions including juvenile chronic arthritis and Still's disease
 
• Polymyalgia rheumatica
 
• Spondyloarthritis, including ankylosing spondylitis, reactive arthritis (Reiter's Syndrome) and undifferentiated spondyloarthritis
 
• Psoriatic arthropathy
 
• Relapsing polychondritis
 
• Mixed connective tissue disorder
 
	
 
• Psoriasis
 
• Vitiligo
 
• Erythema nodosum
 
• Autoimmune bullous skin diseases (including pemphigus, pemphigoid and dermatitis herpetiformis)
 
• Alopecia areata
 
• Lichen planus
 
• Sweet's syndrome
 
• Localized Scleroderma (Morphea)
 

Vasculitides	Blood disorders	Others

 
• Large vessels vasculitis including: giant cell arteritis such as Takayasu's arteritis and temporal arteritis.
 
• Medium sized and/or small vessels vasculitis including: polyarteritis nodosa, Kawasaki's disease, microscopic polyangiitis, Wegener's granulomatosis, Churg-Strauss syndrome (allergic granulomatous angiitis), Buerger's disease (thromboangiitis obliterans), necrotizing vasculitis and anti-neutrophil cytoplasmic antibody (ANCA) positive vasculitis (type unspecified), Henoch-Schonlein purpura, Behcet's syndrome, leukocytoclastic vasculitis.
 
	
 
• Autoimmune hemolytic anemia
 
• Autoimmune thrombocytopenia
 
• Antiphospholipid syndrome
 
• Pernicious anemia
 
• Autoimmune aplastic anemia
 
• Autoimmune neutropenia
 
• Autoimmune pancytopenia
 
	
 
• Autoimmune glomerulonephritis (including IgA nephropathy, glomerulonephritis rapidly progressive, membranous glomerulonephritis, membranoproliferative glomerulonephritis, and mesangioproliferative glomerulonephritis)
 
• Ocular autoimmune diseases (including autoimmune uveitis and autoimmune retinopathy)
 
• Autoimmune myocarditis/cardiomyopathy
 
• Sarcoidosis
 
• Stevens-Johnson syndrome
 
• Sjögren's syndrome
 
• Idiopathic pulmonary fibrosis
 
• Goodpasture syndrome
 
• Raynaud's phenomenon
 

